### **Rationale for the Exclusion Criteria**

- (1) The impact of AbbVie DAAs on pregnancies is unknown.
- (5, 7 – 10) To ensure safety of the subjects throughout the study.
- (3, 4, 6) To avoid bias for the evaluation of efficacy and safety by concomitant use of other medications.
- (2, 11) To exclude subjects with viral infection other than HCV genotype 1.

### **5.2.3 Prior and Concomitant Therapy**

Any medication or vaccine (including over-the-counter or prescription medicines, vitamins and/or herbal supplements) that the subject is receiving at the time of enrollment, or receives during the study, must be recorded along with the reason for use, date(s) of administration including start and end dates, and dosage information including dose, route and frequency.

All medications will be recorded until 30 days following the last dose of study drugs. Only anti-HCV medications and concomitant medications relevant to SAE of death will be collected thereafter.

The AbbVie study-designated physician should be contacted if there are any questions regarding concomitant or prior therapies.

---

### **5.2.3.1 Prior HCV Therapy**

Subjects may be either treatment-naïve or IFN-based therapy (IFN or pegIFN monotherapy, IFN/RBV or pegIFN/RBV) treatment-experienced. Prior or current use of any investigational or commercially available anti-HCV agents other than IFN or RBV, including telaprevir, boceprevir, sofosbuvir, simeprevir or an investigational agent, excludes a subject from this study. Subjects who previously participated in trials of investigational anti-HCV agents may be enrolled if they can produce documentation that they received only placebo.

### **5.2.3.2 Concomitant Therapy**

Subjects must be able to safely discontinue any prohibited medications within 2 weeks or 10 half-lives of the medication whichever is longer, prior to initial study drug administration. Subjects must be consented prior to discontinuing any prohibited medications for the purpose of meeting study inclusion criteria.

The investigator or a qualified designee should confirm that concomitant medication can be safely administered with DAAs (including ritonavir) and RBV. Some medications may require dose adjustments due to potential for drug-drug interactions. The investigator or qualified designee should review the locally approved labels for concomitant medication(s), ribavirin and ritonavir and, where available, ABT-450, ABT-267, and ABT-333 and utilize the drug-drug interactions (DDI) tool that will be provided by the sponsor to screen concomitant medications at each visit for potential DDIs with study drugs. The investigator or qualified designee should document their DDI review in the subject's source or print report and place in subject's source documents.

Management of hematologic growth factor therapy is the responsibility of the investigator; growth factors will not be provided by AbbVie, and AbbVie will not reimburse for the expense of growth factors or their use.

Investigators should refer to the package inserts for erythropoiesis stimulating agents for additional information regarding their use.

Prior to enrollment, subjects should agree to practice two effective methods of birth control while receiving study drugs starting with Study Day 1 for 30 days after stopping study drug or for 7 months after stopping study drug if receiving RBV. Subjects using ethinyl estradiol-containing medications (including combination oral contraceptives) have a higher risk for elevated ALT levels. Subjects using these medications must discontinue them at least 2 weeks prior to study drug administration or 10 half-lives (if known), whichever is longer. Subjects may replace the ethinyl estradiol-containing contraceptive with a progestin-only hormonal contraceptive method.

During the Post-Treatment Period, investigators should reassess concomitant medications. Subjects may resume revert to pre-study doses, at a minimum of 2 weeks following discontinuation of study drugs.

### **5.2.3.3 Prohibited Therapy**

In addition to the medications listed above in [Table 6](#), use of known moderate or strong inducers of CYP3A or strong inhibitors or inducers of CYP2C8 is prohibited within 2 weeks or 10 half-lives of the medication, whichever is longer, prior to the initial dose of study drugs and through the first 2 weeks after the subject has completed study drugs in the Treatment Period.

The investigator or qualified designee should refer to the RBV labeling and DDI tool for a list of prohibited medications. The investigator or qualified designee should document their DDI review in the subject's source or print report and place in subject's source documents. Anti-HCV medications other than those specified in the protocol will not be allowed during the Treatment Period of the study. Some medications may require dose adjustments due to potential for drug-drug interactions.

During the Post-Treatment Period, investigators should reassess concomitant medications. Subjects may resume revert to pre-study doses, at a minimum of 2 weeks following discontinuation of study drugs, if applicable.

**5.3 Efficacy: Pharmacokinetic and Safety Assessments/Variables**

**5.3.1 Efficacy and Safety Measurements Assessed and Flow Chart**

**Table 7. Study Activities**

Activity	Treatment Period (TP)						End of Treatment (EOT) (Week 12 or 24) or Treatment D/C b,c	Post-Treatment (PT) Period
	Screening	Day 1 a	Week 2	Week 4	Week 12 b			
Informed Consent e	X							
Provide RBV Medication Guide f	X							
Medical History	X	X g						
Physical Exam h	X	X						
ECG	X							
Vital Signs, Weight and Height	X i	X	X	X	X	X	X	X
Pregnancy Test [serum (s) urine (u)] j	X (s)	X (u)		X (u)	X (u)	X (u)	X (u)	X k
Hematology/Chemistry/Urinalysis/Coagulation Panel	X	X	X	X	X	X		
FSH (all females)	X							
HBsAg, Anti-HCV Ab, Anti-HIV Ab	X							
HCV Genotype and Subtype	X							
IL28B Sample	X							
Child-Pugh Score l	X							
Pharmacogenetic DNA (optional) m		X						

**Table 7. Study Activities (Continued)**

Activity	Screening	Treatment Period (TP)						End of Treatment (EOT) (Week 12 or 24) or Treatment D/C b,c	Post-Treatment (PT) Period
		Day 1 a	Week 2	Week 4	Week 12 b				
Liver Ultrasound n	X						X	X n	
Concomitant Medication Assessment o	X	X	X	X	X	X	X	X p	
Patient Reported Outcomes (SF-36v2 and FACIT-F) q		X		X	X	X	X	X	
Adverse Event Assessment	X	X	X	X	X	X	X	X p	
Study Drugs Dispensed r		X		X	X	X			
Study Drug Returned for IRT Reconciliation				X	X	X	X b		
HCV RNA Samples	X	X	X	X	X	X	X	X	
HCV Resistance Sample		X	X	X	X	X	X	X	
Liver Biopsy, FibroScan or FibroTest for liver fibrosis assessment s	X	X			X	X	X	X	
Archive Samples (Plasma and Serum)		X	X	X	X	X	X	X	
Assignment of Subject Number via IRT	X								
Enrollment		X							
Assessment of Clinical Outcomes t			X	X	X	X	X	X	

**Table 7. Study Activities (Continued)**

Activity	Treatment Period (TP)						Post-Treatment (PT) Period
	Screening	Day 1 a	Week 2	Week 4	Week 12 b	End of Treatment (EOT) (Week 12 or 24) or Treatment D/C b,c	
Clinical Assessment of Liver Decompensation		X					PT Weeks 4 d , 12, 24, 52, 104, 156, 208, 260 or PT D/C e
Total Insulin		X			X	X	X u

Wk = Week; D/C = Discontinuation

- a. All procedures to be performed prior to first dose.
- b. Treatment Duration Study Visits:
  - Subjects assigned to 12 weeks of treatment will complete the procedures and return drug from the screening visit through the End of Treatment Week 12/ D/C visit procedures. Subjects will complete EOT Week 12 visit procedures instead of completing a TP Week 12 visit.
  - Subjects assigned to 24 weeks of treatment will complete the procedures and return drug from the screening visit through the EOT Week 24/D/C visit procedures at Week 24. Subjects will complete a TP Week 12 Study Visit as an interim visit.
  - Study drug returned for IRT Reconciliation at TP Week 24 is only applicable to subjects who will receive treatment for 24 weeks.
- c. Subjects that prematurely discontinue from the Treatment Period should return to the site to complete the Treatment D/C visit procedures. Subjects that prematurely discontinue from the Post-Treatment Period should return to the site to complete the PT D/C visit procedures.
- d. Study procedures at PT Week 4 are the same as for the remaining PT visits with the exception that FibroScan and Liver ultrasound should not be conducted.
- e. Subjects will need to sign an informed consent for the study (prior to performing any screening or study-specific procedures).
- f. RBV Medication Guide where applicable/locally available.
- g. Medical history will be updated at the Day 1 Visit. This updated medical history will serve as the baseline for clinical assessment.
- h. A symptom-directed physical examination may be performed at any other visit, when necessary.
- i. Height will be measured at Screening only.

**Table 7. Study Activities (Continued)**

- j. Female subjects with a documented history of bilateral tubal ligation, bilateral oophorectomy or hysterectomy or who are confirmed to be post-menopausal do not require pregnancy testing throughout the trial. A positive urine pregnancy test requires a confirmatory serum test. (Refer to Section 5.3.1.1 [Pregnancy Test] for additional details.) Monthly urine pregnancy testing is required for women of childbearing potential who receive RBV for seven months (or per local RBV label) after end of treatment. Females of childbearing potential that were treated with DAAs only in the Treatment Period should have urine pregnancy testing done through Post-Treatment Week 4.
- k. Urinalysis will not be conducted after the PT Week 4 Visit.
- l. Applies only to subjects with cirrhosis or suspected cirrhosis. The Child-Pugh score will be calculated in the EDC RAVE system. Subjects who were considered to be non-cirrhotic at the Screening Visit but identified as cirrhotic (according to definitions listed in Section 5.1) during the screening period will return to the site prior to the baseline visit for Child-Pugh assessment.
- m. Verify the subject has given consent for the pharmacogenetic sample. If the optional pharmacogenetic sample is not collected on Study Day 1, it may be collected at any other visit during the study.
- n. For subjects with compensated cirrhosis:
- Subjects receiving 12 weeks of treatment will have a liver ultrasound performed at the screening visit and all PT visits except PT Week 4.
  - Subjects receiving 24 weeks of treatment will have a liver ultrasound performed at the screening visit, Week 24 Visit, and all PT visits except the PT Week 4 and PT Week 12.
- For subjects without cirrhosis:
- Liver ultrasound will be performed at the screening visit, PT Week 52, PT Week 156 and PT Week 260.
- Subjects with a historical negative liver ultrasound, CT or MRI (within 3 months prior to screening) are not required to undergo a screening ultrasound.
- o. The DDI tool provided by the sponsor should be utilized to evaluate the concomitant medications.
- p. AE and concomitant medications will not be collected after the PT Week 4 Visit. Only anti-HCV medications and concomitant medications relevant to SAE of death will be collected after the PT Week 4 Visit.
- q. SF-36v2 and FACIT-F should be administered as the first study procedure at each visit and in the order listed.
- r. Study drugs dispensed at Week 12 only for subjects in the 24-week arm.
- s. Historical or screening liver biopsy, FibroScan or FibroTest results will be used to determine the presence or absence of cirrhosis for the purpose of treatment assignment. FibroTest will be performed at Day 1, PT Week 12 during the post-treatment period. At sites where FibroScan is available, subjects will have FibroScan performed at Screening, End-of-Treatment Visit, and at all Post-Treatment Visits with the exception of PT Week 4.

**Table 7. Study Activities (Continued)**

- t. Clinical Outcome events that occur during the Treatment Period through PT Week 4 are to be recorded and documented in the eCRF as an AE/SAE in addition to being captured in the Clinical Outcome eCRF(s). Clinical outcome events that occur after the PT Week 4 are to be recorded in the Clinical Outcome eCRFs only, except when the clinical outcome is death, in which case the SAE eCRF would also need to be completed.
- u. Total Insulin will not be obtained at PT Week 4, 12, and 24.

### **5.3.1.1 Study Procedures**

The study procedures outlined in [Table 7](#) are discussed in detail in this section with the exception of the assessment of concomitant medications (Section [5.2.3](#)), and the collection of adverse event information (Section [6.4](#)). All study data will be recorded in the subject's source documentation and then on the appropriate eCRFs, with the exception of laboratory data which will be provided to the Sponsor electronically from the individual laboratory(ies).

#### **Informed Consent and RBV Information**

Signed study-specific informed consent will be obtained from the subject before any study procedures are performed. All subjects will be given the RBV Medication Guide (where applicable/locally available). Details about how informed consent will be obtained and documented are provided in Section [9.3](#).

#### **Medical History**

A complete medical history, including history of tobacco and alcohol use, will be taken at Screening. The subject's medical history will be updated at the Study Day 1 Visit. This updated medical history will serve as the baseline for clinical assessment.

#### **Physical Examination**

A complete physical examination will be performed at the Screening Visit and at Study Day 1. A symptom-directed physical examination may be performed at any other visit, when necessary.

The physical examination performed at the Study Day 1 Visit will serve as the baseline physical examination for clinical assessment. Any significant physical examination findings after the first dose will be recorded as adverse events.

### **Vital Signs, Weight and Height**

Body temperature, blood pressure, pulse and body weight will be measured at each study visit as specified in [Table 7](#) or upon subject discontinuation. Blood pressure and pulse rate will be measured after the subject has been sitting for at least 3 minutes. The vital signs performed on Study Day 1 will serve as the baseline for clinical assessment. The subject will wear lightweight clothing and no shoes during weighing.

Height will be measured only at Screening; the subject will not wear shoes.

### **12-lead Electrocardiogram**

A 12-lead resting ECG will be obtained at the Screening Visit and when clinically needed.

The ECG should be obtained prior to the blood collection.

The ECG will be evaluated by an appropriately trained physician at the site ("local reader"). The local reader from the site will interpret, sign, and date ECG tracings and will provide his/her global interpretation as a written comment on the tracing using the following categories:

- Normal ECG
- Abnormal ECG – not clinically significant
- Abnormal ECG – clinically significant

Only the local reader's assessment of the ECG tracing will be collected on case report forms, entered into the database and summarized. The automatic machine reading (i.e., machine-generated measurements and interpretation that are automatically printed on the ECG tracing) will not be collected.

### **Pregnancy Test**

Pregnancy tests are not required for female subjects with documented prior bilateral tubal ligation, bilateral oophorectomy or hysterectomy or for subjects who are confirmed to be

postmenopausal. Confirmation of postmenopausal status measured by FSH will be obtained at the Screening Visit only for all female subjects.

For females of childbearing potential:

- A serum pregnancy test will be performed at the Screening Visit only and sent to the central laboratory for analysis.
- Pregnancy testing will be performed as specified in [Table 7](#) regardless of treatment regimen.
- Females of childbearing potential that were treated with DAAs only in the Treatment Period should have urine pregnancy testing done through Post-Treatment Week 4.
- Subjects that receive a RBV containing regimen will have pregnancy tests performed monthly throughout the Treatment Period and for a minimum of 7 months after the discontinuation of RBV, or according to the local RBV label and/or local treatment guidelines for RBV.
- Urine pregnancy testing will be performed on-site during the study visit if there is a scheduled visit. If there is not a scheduled study visit, subjects may either have pregnancy testing performed at the site as an unscheduled study visit using an unscheduled test kit or a urine pregnancy test may be conducted by the subject at home with a pregnancy test kit provided by the site. If a urine pregnancy test is performed at home, site personnel should contact these female study subjects to capture the results of any study-related pregnancy tests in the source records only.
- If a urine pregnancy result is positive a confirmatory hCG serum test should be collected and sent to the central lab.

### **Hepatitis and HIV Screen**

HBsAg (hepatitis B surface antigen), anti-HCVAb and anti-HIV Ab will be performed at Screening. A positive anti-HIV Ab test must be confirmed. The investigator must discuss any local reporting requirements to local health agencies with the subject. The site will report these results per local regulations, if necessary.

### **Clinical Laboratory Samples**

Clinical Laboratory Samples will be obtained at a minimum for the clinical laboratory tests outlined in [Table 8](#) at the visits specified in [Table 7](#). Blood samples for serum chemistry tests should be collected following a minimum 8-hour at fast on the following visits: Day 1, End of Treatment Visit, and PT Week 52, 104, 156, 208, and 260. The remaining visits may be non-fasting. Subjects whose visits occur prior to the morning dose of study drug should be instructed to fast after midnight. Subjects whose visits occur following the morning dose of study drug should be instructed to fast after breakfast until the study visit occurs.

A certified central laboratory will be utilized to process and provide results for the clinical laboratory tests.

Instructions regarding the collection, processing, and shipping of these samples will be provided by the central laboratory chosen for this study. The certified laboratory chosen for this study is ICON. Depending on the location of the study site, samples may be sent to one of the following addresses:

ICON Central Laboratories, Inc.  
[name]  
[name]  
USA

ICON Central Laboratories, Inc.  
[name]  
[name]  
Ireland

ICON Central Laboratories, Inc.  
[name]  
[name]  
[name]

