CALCIUM, IONIZED, LOW	<LLN – 1.0 mmol/L	<1.0 – 0.9 mmol/L	<0.9 – 0.8 mmol/L	<0.8 mmol/L
CALCIUM, IONIZED, HIGH	>ULN – 1.5 mmol/L	>1.5 – 1.6 mmol/L	>1.6 – 1.8 mmol/L	>1.8 mmol/L

Clinical Toxicity Grades for HCV Studies (Continued)				
	GRADE 1 TOXICITY	GRADE 2 TOXICITY	GRADE 3 TOXICITY	GRADE 4 TOXICITY
CHOLESTEROL HIGH	>ULN – 300 mg/dL >ULN – 7.75 mmol/L	>300 – 400 mg/dL >7.75 – 10.34 mmol/L	>400 – 500 mg/dL >10.34 – 12.92 mmol/L	>500 mg/dL >12.92 mmol/L
CREATININE	1.5 – 1.7 mg/dL	1.8 – 2.0 mg/dL	2.1 – 2.5 mg/dL	>2.5 mg/dL or requires dialysis
GLUCOSE, SERUM, LOW	<LLN – 55 mg/dL <LLN – 3.0 mmol/L	<55 – 40 mg/dL <3.0 – 2.2 mmol/L	<40 – 30 mg/dL <2.2 – 1.7 mmol/L	<30 mg/dL <1.7 mmol/L
GLUCOSE, SERUM, HIGH (Fasting)	>ULN – 160 mg/dL >ULN – 8.9 mmol/L	>160 – 250 mg/dL >8.9 – 13.9 mmol/L	>250 – 500 mg/dL >13.9 – 27.8 mmol/L	>500 mg/dL >27.8 mmol/L or acidosis
MAGNESIUM, SERUM, LOW	<LLN – 1.2 mg/dL <LLN – 0.5 mmol/L	<1.2 – 0.9 mg/dL <0.5 – 0.4 mmol/L	<0.9 – 0.7 mg/dL <0.4 – 0.3 mmol/L	<0.7 mg/dL <0.3 mmol/L
MAGNESIUM, SERUM, HIGH	>ULN – 3.0 mg/dL >ULN – 1.23 mmol/L		>3.0 – 8.0 mg/dL >1.23 – 3.30 mmol/L	>8.0 mg/dL >3.30 mmol/L
PHOSPHATE, SERUM, LOW	<LLN – 2.5 mg/dL <LLN – 0.8 mmol/L	<2.5 – 2.0 mg/dL <0.8 – 0.6 mmol/L	<2.0 – 1.0 mg/dL <0.6 – 0.3 mmol/L	<1.0 mg/dL <0.3 mmol/L
POTASSIUM, SERUM, LOW	<LLN – 3.0 mmol/L		<3.0 – 2.5 mmol/L	<2.5 mmol/L
POTASSIUM, SERUM, HIGH	>ULN – 5.5 mmol/L	>5.5 – 6.0 mmol/L	>6.0 – 7.0 mmol/L	>7.0 mmol/L
PROTEIN, SERUM, LOW	5.5 – 6.0 g/dL	<5.5 – 5.0 g/dL	<5.0 g/dL	
SODIUM, SERUM, LOW	<LLN – 130 mmol/L		<130 – 120 mmol/L	<120 mmol/L
SODIUM, SERUM, HIGH	>ULN – 150 mmol/L	>150 – 155 mmol/L	>155 – 160 mmol/L Hospitalization may be indicated	>160 mmol/L
TRIGLYCERIDES HIGH (fasting)	150-300 mg/dL; 1.71 – 3.42 mmol/L	>300-500 mg/dL; >3.42-5.7 mmol/L	>500-1000 mg/dL; >5.7 – 11.4 mmol/L	>1000 mg/dL; >11.4 mmol/L
URIC ACID, SERUM, HIGH	7.5 – 10.0 mg/dL	10.1-12.0 mg/dL	12.1-15.0 mg/dL	>15.0 mg/dL

Clinical Toxicity Grades for HCV Studies (Continued)				
	GRADE 1 TOXICITY	GRADE 2 TOXICITY	GRADE 3 TOXICITY	GRADE 4 TOXICITY
ENZYMES				
ALT/SGPT	>ULN - 3.0 x ULN	>3.0 - 5.0 x ULN;	>5.0 – 20.0 x ULN	>20.0 x ULN
AST/SGOT	>ULN - 3.0 x ULN	>3.0 - 5.0 x ULN;	>5.0 – 20.0 x ULN	>20.0 x ULN
ALKALINE PHOSPHATASE	>ULN – 2.5 x ULN	>2.5 – 5.0 x ULN	>5.0 – 20.0 x ULN	>20.0 x ULN
AMYLASE	>ULN – 1.5 x ULN	>1.5 – 2.0 x ULN	>2.0 – 5.0 x ULN	>5.0 x ULN

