Week 12	84	57 to 126
Week 24 ^b	168	127 to 182
Final Treatment Visit ^c		2 to ≤ 2 days after last dose of study drug

a. Day of first dose of study drug.

b. Applicable to subjects with 24 weeks of treatment.

c. The last value within the window will be used to define the final on-treatment value. The upper bound of this Final window is Study Drug End Day ≤ 2.

Note: The result closest to the scheduled time point will be used. Data must also be ≤ 2 days of the last dose of study drug. Total Insulin is measured at baseline, Week 12, Week 24 (for subjects on 24-week treatment regimen only), or EOT, and will use those visit windows as defined above.

Table 6. Laboratory Data and Vital Sign Visit Windows (Post-Treatment Period)

Scheduled Time	Nominal Day (Study Drug End Day)	Time Window (Study Drug End Days Range)
Post-Treatment Week 4	28	3 to 56
Post-Treatment Week 12	84	57 to 126
Post-Treatment Week 24	168	127 to 266
Post-Treatment Week 52	364	267 to 546
Post-Treatment Week 104	728	547 to 910
Post-Treatment Week 156	1092	911 to 1274
Post-Treatment Week 208	1456	1275 to 1638
Post-Treatment Week 260	1820	1639 to 2002
Final Post-Treatment Visit ^a		> 2 days after last dose of study drug

a. The last value within the Post-Treatment Period window will be used to define the final post-treatment value.

Note: The result closest to the scheduled time point will be used. Data must also have Study Drug End Day > 2. Vital signs and hematology, chemistry, urinalysis, and coagulation panels are collected at every Post-Treatment Period visit. Urinalysis is not conducted after PT Week 4. Total Insulin is collected at Post-Treatment Weeks 52, 104, 156, 208, and 260 and will use those visit windows as defined above. FibroTest samples are collected at Post-Treatment Weeks 12 (or upon study discontinuation) and will use those visit windows as defined above.

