11.3.2 Statistical Methods

Clinical laboratory tests will be summarized at each visit during the Treatment Period. The baseline value will be the last measurement on or before the day of the first dose of study drug. This same baseline value will be used for all change from baseline tables in the Treatment Period and Post-Treatment Periods.

Mean changes from baseline to each post-baseline visit, including applicable post treatment visits, will be summarized for each protocol-specified laboratory parameter with the baseline mean, visit mean, change from baseline mean, standard deviation, and median.

Laboratory data values will be categorized as low, normal, or high based on normal ranges of the laboratory used in this study. Shift tables from baseline to minimum value, maximum value, and final values during the Treatment Period (Study Drug End Day \leq 2) will be created. The shift tables will cross tabulate the frequency of subjects with baseline values below/within/above the normal range versus minimum/maximum/final values below/within/above the normal range.

The number and percentage of subjects with post-baseline values during the Treatment Periods meeting the specified criteria for Potentially Clinically Significant (PCS) laboratory values (defined in [Table 8](#) and [Table 9](#)) will be summarized. A post-baseline value must be more extreme than the baseline value to be considered a PCS finding. A separate listing will be provided that presents all lab values for the subjects meeting PCS criteria during treatment.

For hemoglobin and the liver function tests (LFTs) of alkaline phosphatase and total bilirubin, the number and percentage of subjects with a maximum Common Terminology Criteria for Adverse Events (CTCAE) Grade of 1, 2, 3, or 4 (see definitions in [Table 10](#)) at any post-baseline visit (regardless of the baseline value) through the end of treatment (i.e., Final Treatment Value) will be summarized. All LFT tables will include summary rows for the number and percentage of subjects with at least Grade 2 and at least Grade 3 laboratory abnormalities. The hemoglobin table will include a summary row for the number and percentage of subjects with at least a Grade 2 laboratory abnormality.

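### Glucose and triglyceride change, shift-to-high and PCS summaries set possibly non-fasting visits against a fasting baseline, and Week 12 insulin pools two sampling conditions

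*Protocol*

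**What the plan says.** Protocol 5.3.1.1 (Clinical Laboratory Samples) asks for at least 8 hours of fasting before serum chemistry at "Day 1, End of Treatment Visit, and PT Week 52, 104, 156, 208, and 260". It then adds: "The remaining visits may be non-fasting". Protocol Table 7 also schedules chemistry at Weeks 2, 4 and 12, and the note under SAP Table 6 has it at every post-treatment visit.

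SAP 11.3.2 plans the following: "Mean changes from baseline to each post-baseline visit, including applicable post treatment visits, will be summarized for each protocol-specified laboratory parameter". The same section builds shift tables from baseline to the minimum, maximum and final value, and counts PCS values. Both of these are confined to the Treatment Period. None of the three analyses is restricted or stratified by fasting status.

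SAP Table 9 sets the high PCS limits at more than 250 mg/dL for glucose and more than 500 mg/dL for triglycerides, with no fasting qualifier. In Protocol Appendix C the same values are the lower bounds of Grade 3, in rows that are labelled fasting. The triglyceride label begins "TRIGLYCERIDES HIGH (fasting".

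For insulin, the note under SAP Table 5 says "Total Insulin is measured at baseline, Week 12, Week 24 (for subjects on 24-week treatment regimen only), or EOT", and Protocol Table 7 note u says "Total Insulin will not be obtained at PT Week 4, 12, and 24". On the Week 12 visit of 24-week subjects, Table 7 note b says: "Subjects will complete a TP Week 12 Study Visit as an interim visit". For 12-week subjects, Week 12 is the EOT visit.

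**The concern.** A change from baseline is interpretable only if both samples were taken under the same conditions. Here the Day 1 sample is fasting, and most of the on-treatment samples need not be. A meal raises triglycerides and glucose. A table that follows the SAP exactly can therefore show a rise at Weeks 2 and 4 that has nothing to do with study drug. The maximum used in the shift tables and the PCS count both draw on those samples.

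The design offers no protection. Protocol 5.6.1 states that there is no control group, so a shared meal effect cannot cancel. Protocol 5.3.1.3 has the morning dose taken with food, so an on-treatment sample drawn after that dose follows a meal. Protocol 6.7.2 does not require confirmation of Grade 3 or higher triglycerides, or of glucose in subjects with a history of diabetes, so a post-meal value may stand unrepeated. At stake is the reading of the metabolic safety tables.

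**Working it through.** The plan states no figure on this point to reproduce. The check is a count of visits, a comparison of limits, and an illustration under stated assumptions.

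**1. Visits.** The schedule comes from Protocol Table 7 and the notes under SAP Tables 5 and 6; the fasting list comes from Protocol 5.3.1.1.

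| Possibly non-fasting, of all scheduled | 12-week subjects | 24-week subjects |
|---|---|---|
| Chemistry, on treatment | 2 of 3 (Weeks 2, 4) | 3 of 4 (Weeks 2, 4, 12) |
| Chemistry, post-treatment | 3 of 8 (PT Weeks 4, 12, 24) | 3 of 8 |
| Chemistry, all post-baseline | 5 of 11 | 6 of 12 |
| Insulin, all post-baseline | 0 of 6 | 1 of 7 (interim Week 12) |

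**2. Where these visits enter.** The on-treatment visits enter all three SAP summaries. The three post-treatment visits enter only the mean changes, because the shift and PCS tables stop at the end of the Treatment Period.

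**3. Limits.** SAP Table 9 and the fasting Grade 3 rows of Appendix C agree at 250 mg/dL (13.9 mmol/L) for glucose and 500 mg/dL (5.7 mmol/L) for triglycerides.

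**4. The PCS safeguard.** SAP Table 9 requires a value to be more extreme than baseline. With a fasting baseline, a post-meal value passes that test easily, so the rule does not remove a meal effect.

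**5. Illustration of size.** The documents give no distributions and no meal effect, so every input here is an assumption. Values are log-normal with no true change. Weeks 2 and 4 are both non-fasting in every subject, and a meal multiplies the value by m. Triglycerides have median 120 mg/dL and log-SD 0.45 between and 0.25 within subjects. Glucose has median 98 mg/dL and log-SD 0.22 and 0.08.

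False mean rise at one visit = (m − 1) × median × exp[(between² + within²)/2].

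- Triglycerides: 120 × exp(0.265/2) = 137.0 mg/dL. For m = 1.15, 1.3 and 1.5 the rise is about 21, 41 and 68 mg/dL.
- Glucose: 98 × exp(0.0548/2) = 100.7 mg/dL. For m = 1.1, 1.2 and 1.4 the rise is about 10, 20 and 40 mg/dL.

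If only half the subjects had eaten, these rises would halve. PCS counts were simulated over Weeks 2, 4 and EOT (400,000 subjects):

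- Triglycerides: 1.1%, 2.0% and 3.8%, against 0.6% with no meal effect.
- Glucose: 0.03%, 0.10% and 0.8%, against 0.01%.

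At the fasting EOT visit the false mean change is about 0.

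**6. Insulin.** The SAP Week 12 window is days 57 to 126. It takes the EOT sample of a 12-week subject and the interim sample of a 24-week subject, and SAP 5.1.3 presents safety data for all subjects together. The interim visit is not on the fasting list. Protocol Table 8 places insulin under additional tests, while SAP 11.3.1 counts it among the chemistry variables. Whether the serum chemistry fast covers insulin at all is therefore not explicit.

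**The case against.** The case against has force on several points, and a reader could easily infer more than the documents support.

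- **Insulin generally affected.** It is not. Insulin is not drawn at Weeks 2 or 4, nor at PT Weeks 4, 12 or 24, and Table 9 gives it no PCS limit. Only the pooled Week 12 summary is in question.
- **Post-treatment samples inflate the PCS and shift tables.** They never enter them.
- **The SAP applies fasting grades.** Table 9 carries no such label and departs from Grade 3 elsewhere: alkaline phosphatase is flagged above 1.5 × ULN, where Grade 3 begins above 5 × ULN. SAP Table 10 does not grade glucose or triglycerides. The match of limits is a fact; that the limits were meant as fasting grades is an inference.
- **A fall between PT Weeks 24 and 52 would be read as a benefit of SVR, or Week 12 insulin would confound fasting with cirrhosis.** The SAP plans no comparison of those two visits, no comparison of these tests by SVR12 status, and no contrast of Week 12 insulin by cirrhosis or treatment duration.
- **The rises will occur.** Fasting is optional at these visits, not forbidden. The instruction "Subjects whose visits occur following the morning dose of study drug should be instructed to fast after breakfast until the study visit occurs" is not tied to named visits, so some of these samples may be fasting.
- **Restricting to fasting visits loses safety data.** Dropping every Week 2 and 4 value would discard high values worth reviewing, and also low glucose, which a recent meal does not falsely create.

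These points narrow the concern and shape the fix. They do not answer the core: the planned summaries compare unlike samples, and nothing in the SAP marks which ones. Nor does a visit name prove a fast. A fast that begins after breakfast may fall short of 8 hours, and under SAP 6.1.1 a missing Day 1 value is replaced by an earlier one, possibly a non-fasting Screening sample.

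**Conclusion.** The concern holds for glucose and triglycerides in three SAP 11.3.2 summaries: mean change, shift to the on-treatment maximum, and high-side PCS counts. These can show apparent rises that reflect meals. Comparisons at EOT and PT Weeks 52 to 260 are fasting against fasting and stand as planned, provided that the baseline is the Day 1 sample and the fast was kept. For insulin the point is limited to pooling at Week 12.

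The size cannot be derived from the documents. It depends on how many subjects have eaten and how recently. In the illustration the false mean rises are noticeable for both tests. The PCS effect is appreciable for triglycerides, but for glucose it is small unless the meal factor is large. This is a matter of descriptive safety tables: the clinical outcome, SVR12 and FibroScan analyses do not use these values. It is worth correcting because the tables as specified can mislead and the correction is cheap.

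**What to change.** In SAP 11.3.2:

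1. Base the glucose and triglyceride mean-change, shift-to-high and high-side PCS summaries on the fasting visits listed in Protocol 5.3.1.1 or, better, on samples recorded as fasting.
2. Show the possibly non-fasting visits separately and labelled as such, including values above the Table 9 limits, so that no high value is lost from safety review.
3. Keep low-glucose PCS over all visits.
4. Report Week 12 insulin separately for 12-week subjects (EOT) and 24-week subjects (interim), or add the interim Week 12 visit to the fasting list. State whether the fasting rule covers insulin.
5. State in Table 9 to which samples the glucose and triglyceride limits apply.

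The cost is a few sentences, a filter in programming and slightly more tables. Neither document says that fasting status is recorded, so the sample-level option needs that data item. The fasting summary keeps only EOT on treatment (1 of 3 or 1 of 4 chemistry visits) and 6 of 11 or 6 of 12 visits overall. Fewer samples also lower the count in themselves: in the illustration with no meal effect, triglyceride PCS falls from 0.59% over three samples to 0.25% at EOT alone. The labelled table of the other visits must therefore stand beside it.
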